2.3 Benefit/Risk Assessment

It cannot be guaranteed that participants in clinical studies will directly benefit from treatment during participation, as clinical studies are designed to provide information about the safety and effectiveness of an investigational medicine.

MK-3475A may provide an alternative SC dosage form of pembrolizumab that could offer patients an alternate form of administration maintaining the efficacy and safety of IV pembrolizumab with shorter administration time, improved patient convenience, satisfaction, and quality of life.

Pembrolizumab delivered by SC administration is expected to maintain a favorable benefit-risk profile comparable to that of IV administration.

Due to large volume of drug given under the skin, injection reactions are expected with MK-3475A.

IV pembrolizumab is approved for the indications being evaluated in this study. The benefit of MK-3475A is expected to be similar to that of IV pembrolizumab.

Additional details regarding specific benefits and risks for participants participating in this clinical study may be found in the accompanying IBs and informed consent documents.

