3 HYPOTHESES, OBJECTIVES, AND ENDPOINTS

In participants at least 18 years of age with early-stage or advanced/ metastatic solid tumors.

Primary Objective	Primary Endpoint
To evaluate participant preference for MK-3475A SC	Participant preference assessed by response of MK-3475A SC on PPQ question 1
Secondary Objectives	Secondary Endpoints
To evaluate the reasons for preference for MK-3475A SC	Participant responses to PPQ question 3
To evaluate participant satisfaction with route of administration of MK-3475A SC and pembrolizumab IV	Participant responses to the TASQ SC and TASQ IV
To evaluate participants choice of administration for the study Treatment Continuation Period	Participant choice of MK-3475A SC for the study Treatment Continuation Period
To evaluate the safety and tolerability of MK-3475A SC and pembrolizumab IV	AE Discontinuation of study intervention due to AEs
Tertiary/Exploratory Objectives	Tertiary/Exploratory Endpoints
To evaluate healthcare provider preference for route of treatment administration	Healthcare provider preference assessed by HCP questionnaire (HCPQ)

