8.4.1.3 Injection Site Reactions

Any injection-site AE should be reported using standard AE/SAE reporting methods. Injection-site reaction and pain may include, but are not limited to, the following:

- Injection-site redness/erythema
- Injection-site swelling/edema
- Injection-site tenderness/pain/discomfort/irritation
- Injection-site bruising
- Injection-site infection
- Injection-site hard lump (mass, nodule)/induration
- Injection-site inflammation
- Injection-site rash
- Injection-site hematoma/hemorrhage
- Injection-site extravasation
- Injection-site dermatitis
- Injection-site discoloration/pallor

- Injection-site vesicles/ulcers

Any injection-site AEs should be recorded in the AE eCRF.

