8.5 Adverse Events, Serious Adverse Events, and Other Reportable Safety Events

The definitions of an AE or SAE, as well as the method of recording, evaluating, and assessing causality of AE and SAE and the procedures for completing and transmitting AE, SAE, and other reportable safety event reports can be found in Appendix 3.

Adverse events, SAEs, and other reportable safety events will be reported by the participant (or, when appropriate, by a caregiver or surrogate).

The investigator and any designees are responsible for detecting, documenting, and reporting events that meet the definition of an AE or SAE as well as other reportable safety events. Investigators need to document if an SAE was associated with a medication error, misuse, or abuse.

Investigators remain responsible for following up AEs, SAEs, and other reportable safety events for outcome according to Section 8.5.3. The investigator, who is a qualified physician, will assess events that meet the definition of an AE or SAE as well as other reportable safety events with respect to seriousness, intensity/toxicity, and causality.

8.5.1 Time Period and Frequency for Collecting AE, SAE, and Other Reportable Safety Event Information

All AEs, SAEs, and other reportable safety events that occur after the participant provides documented informed consent, but before intervention randomization, must be reported by the investigator if the participant is receiving placebo run-in or other run-in treatment, if the event cause the participant to be excluded from the study, or is the result of a protocol-specified intervention, including, but not limited to washout or discontinuation of usual therapy, diet, or a procedure.

- All AEs from the time of intervention randomization through 30 days after cessation of study intervention must be reported by the investigator.
- All AEs meeting serious criteria, from the time of intervention allocation/randomization through 90 days after cessation of study intervention or 30 days after cessation of study intervention if the participant initiates new anticancer therapy, whichever is earlier, must be reported by the investigator.

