9.5.2 Statistical Methods for Safety Analyses

Safety and tolerability will be assessed by clinical review of AEs and other relevant parameters, including laboratory test results and vital signs. Adverse events will be summarized by MedDRA term, appropriate MedDRA levels (system organ class [SOC] and preferred term [PT]), and when specified by NCI CTCAE grade. For each participant, if multiple incidences of the same adverse events occur, the maximum severity reported will be used in the summaries.

The overall safety endpoints include the number of participants with at least one AE, drug-related AE, serious AE, serious, drug-related AE, Grade 3-5 AE, AEOSI, who discontinue from study intervention due to an AE, or with an AE resulting in death. The number and percentage for injection-site reactions will be provided for participants who receive MK-3475A SC treatment.

The safety evaluation will include a summary of the number and percentage of participants with each type of AE by treatment intervention for cycles 1-3 and cycles 4-6 in the Crossover

Period, and by treatment arm in the overall study. For overall safety endpoints, specific AEs and safety topics of special interest that meet predefined threshold rules, point estimates and 95% CIs for the differences between treatment groups (i.e., treatment interventions for cycles 1-3 in the Crossover Period, treatment interventions for cycles 4-6 in the Crossover Period and treatment arms in the overall study) in the percentages of participants with events will be provided using the M&N method [Miettinen, O. and Nurminen, M. 1985].

The number and percentage of participants with laboratory toxicity grade increased from baseline will be summarized by the post-baseline maximum toxicity grade per CTCAE V5.0 for each gradable laboratory test.

For continuous safety measures, such as change from baseline in laboratory, vital signs, summary statistics for baseline, on-treatment, and change from baseline values will be provided by treatment arm.

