3.5.2.1 Overall Safety Assessment

The overall safety evaluation will include a summary by treatment intervention for cycles 1-3 and cycles 4-6 in the Crossover Period, and by treatment arm in the overall study. An adverse event will be attributed to the treatment received on or before the AE start date. Adverse events that started during the first three cycles of the Crossover Period and continued into subsequent three cycles (even if the AE changed severity grade) will be summarized by the route of administration during which it first occurred. These AEs will be flagged in listings.

The overall safety endpoints include the number and percentage of participants with at least one AE, drug-related AE, serious AE, serious, drug-related AE, Grade 3-5 AE, AEOSI, who discontinue from study intervention due to an AE, or with an AE resulting in death. The number and percentage for injection-site reactions will be provided for participants who receive MK-3475A SC treatment. Point estimates and 95% CIs for the differences between treatment groups (i.e., treatment interventions for cycles 1-3 in the Crossover Period,

treatment interventions for cycles 4-6 in the Crossover Period and treatment arms in the overall study) in the percentages of participants with the event will be provided based on the criteria described below for specific AEs.

The number and percentage of participants with specific AEs will also be provided. Point estimate and 95% CIs for the difference between treatment groups in the percentage of participants with specific AEs will be provided if at least 10% of participants in any treatment group exhibit the event. The threshold of at least 10% of participants was chosen because the population enrolled in this study is in critical condition and usually experiences various AEs of similar types regardless of treatment; events reported less frequently than 10% of participants would obscure the assessment of the overall safety profile and add little to the interpretation of potentially meaningful treatment differences. In addition, difference in the percentage of participants with specific Grade 3 to 5 AEs ($\geq 5\%$ of participants in 1 of the treatment groups) and SAEs ($\geq 5\%$ of participants in 1 of the treatment groups) will also be summarized by point estimate and 95% CIs.

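### Local reactions get a grouped participant-level percentage for MK-3475A SC only; a matching infusion-site row for pembrolizumab IV would allow a like-for-like comparison (minor)

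*SAP*

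**What the plan says.** The secondary safety objective in Protocol Section 3 covers both products: "To evaluate the safety and tolerability of MK-3475A SC and pembrolizumab IV". On local reactions, Protocol 2.3 says: "Due to large volume of drug given under the skin, injection reactions are expected with MK-3475A".

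Protocol 9.5.2 and SAP 3.5.2.1 use the same sentence for the grouped analysis: "The number and percentage for injection-site reactions will be provided for participants who receive MK-3475A SC treatment". In SAP Table 2 the injection-site row is marked for descriptive statistics, and its between-group interval column is blank. There is no infusion-site row.

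On collection, Protocol 8.4.1.3 states "Any injection-site AE should be reported using standard AE/SAE reporting methods" and follows this with 13 example terms, all for the injection site. Protocol 8.5.1 covers both routes: "All AEs from the time of intervention randomization through 30 days after cessation of study intervention must be reported by the investigator".

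On general tabulation, the SAP states "The overall safety evaluation will include a summary by treatment intervention for cycles 1-3 and cycles 4-6 in the Crossover Period", and Protocol 9.5.2 plans "a summary of the number and percentage of participants with each type of AE by treatment intervention for cycles 1-3 and cycles 4-6". Events are coded to system organ class and preferred term. Table 2 has a descriptive row for specific events at any incidence above zero. A specific event earns a between-group interval only when it reaches 10% in a treatment group (5% for serious or Grade 3 to 5 events).

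**The concern.** The trial exists to compare two routes of giving the same drug, so local tolerability is the safety topic where the routes most obviously bear comparison. The plan gives that topic a grouped percentage on one route and only separate preferred-term rows on the other. A reader of the overall safety table would see an SC local-reaction rate with no IV figure beside it.

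The preferred-term rows do not fully repair this. One participant can contribute to several rows (for example pain and bruising), so adding rows can overcount and taking the largest row can undercount. A grouped category can also pass 10% while each of its terms stays below, in which case no interval is produced for any of them.

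The participant-reported measures touch the same subject. PPQ question 3 offers less injection-site pain as a reason for preference, and the TASQ asks about pain, swelling and redness on each route. Adverse-event rates grouped in the same way on both routes would be a natural companion to those answers.

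**Working it through.** **Inputs from the documents**
- 144 randomized, 1:1 (SAP 3.8, Protocol 4.1): 144 / 2 = 72 per arm. In cycles 1-3 this is about 72 on SC (Arm A) and 72 on IV (Arm B).
- About 20% dropout before the C6D1 questionnaire (SAP 3.8).
- Nine participants with injection-site events in the Phase 1 study MK-3475A-C18 (Protocol 2.2.1). No safety denominator is given; that section mentions 81 participants with PK data and 83 with antibody data.
- Interval method: Miettinen-Nurminen, 95% (SAP 3.5.2.1).

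**The plan's own figure.** No planned figure concerns local reactions. The sample-size figures reproduce: 144 × 0.80 = 115.2, and by tumor type 48 × (0.86 + 0.87 + 0.67) = 115.2, against the stated figure of about 115.

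**The 10% rule in participants.** 10% of 72 = 7.2, so a term needs 8 participants (8/72 = 11.1%; 7/72 = 9.7% falls short). If about 115.2 / 2 = 57.6, or 58, per arm remain late in the crossover, the threshold is 6.

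**A plausible SC rate (assumption).** 9/81 = 11.1% and 9/83 = 10.8%, so about 8 of 72. A group of that size only just reaches 10% as a whole. Once spread over several terms with fewer than 8 participants each, no term qualifies for an interval.

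**What a grouped comparison would show (assumed IV counts).**

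| SC | IV | Difference, points | 95% CI |
|---|---|---|---|
| 8/72 | 4/72 | 5.6 | -3.9 to 15.7 |
| 8/72 | 2/72 | 8.3 | 0.0 to 18.1 |
| 8/72 | 0/72 | 11.1 | 5.7 to 20.5 |

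**What the preferred-term rows already give.** Suppose the IV column lists three infusion-site terms with 2, 1 and 1 participants. The number of distinct participants is at least the largest row, 2, and at most the sum, 2 + 1 + 1 = 4. The grouped IV rate is then between 2/72 = 2.8% and 4/72 = 5.6%. The reader can bound the rate but cannot state it, and the two ends correspond to the second and first rows of the table above. With no IV local events at all, the IV column would have no infusion-site entries and the rate would be known to be zero.

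**The case against.** The strongest reply is that the comparison is already largely there. All adverse events on both routes must be reported, and they are tabulated by route within cycles 1-3 and cycles 4-6, so even a single infusion-site event gets a row. A reader might infer from the SC-only sentence that local tolerability of the two routes cannot be compared, or that the plan could not distinguish no IV events from a few. The documents do not support either inference: as the bounds above show, the plan separates those cases. What stands is only that the exact grouped rate and its interval are missing.

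A reader might also infer that the protocol predicts a difference between routes. Section 2.3 says that reactions are expected with the SC product and makes no comparison with IV.

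A third inference is that the list in 8.4.1.3 biases ascertainment toward SC. The list is non-exhaustive guidance on what to report, and Protocol 8.5.2 prefers open-ended, nonleading questioning. One-sided collection is therefore not shown.

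It is also fair to say that this is an estimation study without hypotheses, that the SAP treats safety intervals as descriptive, and that Table 2 omits between-group intervals for other grouped rows such as any adverse event. The missing interval is therefore not peculiar to local reactions, although those other rows do have figures for both routes.

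The TASQ gives a participant-reported comparison by route. SAP 3.5.1 refers both to question 1 and to all 12 questions, which needs reconciling but is a separate matter. In either form it does not supply adverse-event incidence.

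**Conclusion.** The gap is real and minor. The plan gives a grouped participant-level local-reaction percentage for SC and none for IV, although the safety objective names both products. Existing tables bound the IV figure without giving it exactly, and no difference is planned unless a single term crosses a threshold.

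The size is illustrative only. It rests on about 72 participants per route in cycles 1-3, an SC rate near 11% borrowed from the Phase 1 study with an assumed denominator, and assumed IV counts of 0 to 4. Under those assumptions the difference runs from 5.6 to 11.1 points, with intervals that include zero at one end and exclude it at the other. The documents give no IV local-reaction rate, so they cannot say which case is likely.

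The primary endpoint, the sample size and SAP Table 3 do not depend on this point.

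**What to change.** Keep the existing SC injection-site row unchanged. In SAP 3.5.2.1 and Table 2:

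1. Add an infusion-site reaction row for pembrolizumab IV, defined by a MedDRA term list fixed before database lock.
2. Report the percentage of participants with a local administration-site reaction (injection-site terms on SC, infusion-site terms on IV) by route for cycles 1-3 and for cycles 4-6, with the Miettinen-Nurminen difference and 95% CI, labeled as descriptive.
3. Report catheter or vascular-access terms separately, if at all. Blood is drawn every cycle on both routes, so pooling these terms could mix in events unrelated to the route of the drug and could change the SC rate.

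The cost is one term list and one extra table row, with the accompanying interval. The data are already collected and the method is already in the SAP. An SAP amendment before final database lock is the route that the SAP itself provides for such changes.

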3.5.2.2 Assessment of Safety Topics of Special Interest

AEs that are immune-mediated or potentially immune-mediated will be evaluated separately. These events have been characterized consistently throughout the pembrolizumab clinical development program. Point estimates and 95% CIs for between-group difference is not expected to add value to the safety evaluation, and hence only number and percentage of participants with such pembrolizumab AEOSI will be provided, as well as the number and percentage of participants with corticosteroids administration to treat an AEOSI. Summary statistics will be provided for the analysis of time from first dose to the onset of an AEOSI.

[Table 2](#) summarizes analysis strategy for safety endpoints in this study.

Table 2 Analysis Strategy for Safety Parameters

Analysis Part	Safety Endpoint	Descriptive Statistics	95% between-group CI
Overall Safety Assessment	Specific AEs (incidence $\geq 10\%$ of participants in 1 of the treatment groups)	X	X
	Specific Grade 3-5 AE (incidence $\geq 5\%$ of participants in 1 of the treatment groups)	X	X
	Specific serious AE (incidence $\geq 5\%$ of participants in 1 of the treatment groups)	X	X
	Any AE	X	
	Any Grade 3-5 AE	X	
	Any Serious AE	X	
	Any Drug-related AE	X	
	Any Serious and Drug-related AE	X	
	Any Grade 3-5 and Drug-related AE	X	
	Discontinuation from Study Treatment due to AE	X	
	AE that Resulted in Death	X	
	AE that Led to Treatment Interruption	X	
	Injection-site Reaction	X	
	Specific AEs, SOC (incidence $> 0\%$ of participants in any treatment group)	X	
	Change from Baseline Results (lab toxicity shift)	X	
Assessment of safety topics of special interest	Pembrolizumab AEOSI	X	
AE = adverse event; AEOSI = adverse event of special interest; CI = confidence interval; SOC = system organ class			

3.5.3 Demographic and Baseline Characteristics

The comparability of the treatment arms for each relevant demographic and baseline characteristic will be assessed using tables and/or graphs. No statistical hypothesis tests will be performed on these characteristics. The number and percentage of participants screened and randomized and the primary reasons for screening failure and discontinuation will be displayed. Demographic variables, baseline characteristics, primary and secondary diagnoses,

and prior and concomitant therapies will be summarized by treatment arms either by descriptive statistics or categorical tables.

3.6 Interim Analyses

3.6.1 Participant Preference and Satisfaction Measure Interim Analyses

There are no formal interim analyses planned in this study. An interim analysis may be conducted to support a future regulatory submission. The results of this interim analysis will be evaluated by a Sponsor's Executive Oversight Committee.

The final analysis (FA) will occur when approximately 115 participants have evaluable data (i.e., participants who satisfy the FAS population definition stated in Section 3.4.1). This is expected approximately 14.5 months after first participant randomized. All the primary, secondary and exploratory objectives for participant preference and satisfaction measure will be evaluated at FA.

3.6.2 Safety Interim Analyses

There are no planned safety IAs for this study.

3.7 Multiplicity

No multiplicity adjustment is planned as there are no hypotheses in this study.

3.8 Sample Size and Power Calculations

This is an estimation study. This study will randomize 144 participants to treatment arms A or B and will allow estimation of participant preference rate among all evaluable participants with a 95% CI. Assuming ~20% dropout prior to completion of PPQ at C6D1, the expected number of evaluable participants for the primary analysis will be ~115. The ~20% dropout assumption in the overall population was calculated based on the following assumed dropout rates and planned enrollment of ~33% participants for each of the 3 tumor types:

- ~14% dropout rate for adjuvant melanoma population
- ~13% dropout rate for adjuvant renal cell carcinoma population
- ~33% dropout rate for metastatic NSCLC (PD-L1 \geq 50%) population

[Table 3](#) shows the two-sided 95% confidence interval for participant preference rate (PPR) with 115 evaluable participants for different observed PPR based on the method of Clopper and Pearson (1934) [Clopper, C. J. and Pearson, E. S. 1934].

Table 3 Two-sided 95% Confidence Interval for observed PPR with 115 Evaluable Participants

Observed Number of Participants preferring MK-3475A SC	PPR Estimates	95% CI of PPR (%)
63	55%	(45, 64)
69	60%	(50, 69)
75	65%	(56, 74)
80	70%	(60, 78)

3.9 Subgroup Analyses

To determine whether the participant preference rate (PPR) is consistent across various subgroups, the estimate of PPR (with a nominal 95% CI) will be estimated and plotted within each category of the following subgroup variables:

- ECOG PS (0, 1)
- Tumor type (Melanoma, RCC, NSCLC)

For subgroups determined by the levels of a stratification factor, the derived strata based on eCRF collected information (as compared to the IRT/IVRS strata) will be used as the default. If the number of participants in a category of a subgroup variable is less than 10% of the FAS population, the subgroup analysis will not be performed for this category of the subgroup variable, and this subgroup variable will not be displayed in the forest plot.

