4.2 Scientific Rationale for Study Design

KEYTRUDA[®] (MK-3475, pembrolizumab) is approved globally for the treatment of patients across multiple indications. The recommended dose of pembrolizumab in adults is either 200 mg Q3W or 400 mg Q6W administered by IV infusion. MK-3475A SC is a coformulation of pembrolizumab with MK-5180 that is being developed to provide an alternative route of administration with potential benefits for patients. This study will evaluate preference of MK-3475A SC or pembrolizumab IV with a crossover design using Q3W dosing in participants with selected tumor types.

This is an open-label crossover study with pembrolizumab monotherapy. The intent is to evaluate the proportion of participants that prefer SC pembrolizumab over IV pembrolizumab.

A crossover study design allows participants to experience both forms of administration and minimizes variability as each participant serves as their own control. This removes the interparticipant variability from the comparison between groups and the effect of participant-level covariates.

Randomization will be stratified by the following 2 factors, which all have the potential to influence patient preference.

1. ECOG performance status (0 vs 1): ECOG performance status would balance participants in both arms as there may be a higher dropout rate in the less stable participants.
2. Tumor type (melanoma vs RCC vs NSCLC): The oncology clinical studies to date which have outcome measures based on patient preferences have been conducted in a single tumor type [Rummel, M., et al 2017]. In addition, some of these studies included only patients with early-stage disease [Pivot, X., et al 2013] [O'Shaughnessy, J., et al 2021]. Pembrolizumab has multiple indications across tumor types and disease stages, hence it is important to evaluate patient preference on the mode of administration in multiple tumor types and in both the early-stage (adjuvant setting) and metastatic stage. Therefore, the study will plan to enroll approximately 33% each of participants to be treated in:
 - First line metastatic NSCLC harboring PD-L1 \geq 50%
 - Adjuvant indication for intermediate-high or high risk RCC
 - Adjuvant indication of resected Stage IIB, IIC, III melanoma

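### The subgroup section aims to determine whether the preference rate is consistent, but plans no estimate of any between-subgroup difference (minor)

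*SAP*

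**What the plan says.** SAP 3.9 and Protocol 9.9 carry the same text. The stated purpose is "To determine whether the participant preference rate (PPR) is consistent across various subgroups, the estimate of PPR (with a nominal 95% CI"), and the deliverable is that these quantities "will be estimated and plotted within each category of the following subgroup variables": ECOG PS 0 and 1, and "Tumor type (Melanoma, RCC, NSCLC"). A category holding under 10% of the FAS is not analysed, and its variable is left off the forest plot. Neither section plans a difference between categories, an interval for one, a heterogeneity measure, a margin, or a rule for calling rates consistent. Neither names the method for the subgroup intervals; Clopper-Pearson is specified for the overall PPR in SAP 3.5.1.

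Protocol 4.2 explains why three tumor types are enrolled: "it is important to evaluate patient preference on the mode of administration in multiple tumor types and in both the early-stage" and metastatic settings. SAP 3.9 is the only planned analysis of preference by tumor type or stage.

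SAP 3.5, 3.7 and 3.8 describe an estimation study with no hypotheses, no type I error control and no multiplicity adjustment. SAP 3.5.2.1 already uses the Miettinen-Nurminen (M&N) method for between-group differences in adverse event percentages.

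**The concern.** Whether a rate is consistent across groups is a question about the differences between groups. Separate within-group intervals do not answer it. A reader given only the forest plot would have to judge by eye, from the spread of the point estimates and from whether the intervals overlap. At these subgroup sizes, overlap is common even when the true rates differ substantially. The plot also does not show how large a difference remains compatible with the data.

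What is at stake is how the pooled PPR is generalised. The protocol recruits adjuvant melanoma, adjuvant RCC and metastatic NSCLC so that preference can be seen in each. A report that called preference consistent across them, on the planned output alone, would say more than the output shows.

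**Working it through.** **Inputs from the documents (SAP 3.8).** "This study will randomize 144 participants to treatment arms A or B", with "planned enrollment of ~33% participants for each of the 3 tumor types", so 144 / 3 = 48 per type. Assumed dropout is 14% for melanoma, 13% for RCC and 33% for NSCLC.

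**The plan's own figures first.**
- Evaluable: 48 × 0.86 = 41.3 melanoma, 48 × 0.87 = 41.8 RCC and 48 × 0.67 = 32.2 NSCLC. The sum is about 115, agreeing with "Assuming ~20% dropout prior to completion of PPQ at C6D1, the expected number of evaluable participants for the primary analysis will be ~115". I use 41, 42 and 32; pooled adjuvant is 41 + 42 = 83.
- SAP Table 3 (Clopper-Pearson, n = 115): 63, 69, 75 and 80 responders give (45.2, 64.1), (50.4, 69.0), (55.8, 73.9) and (60.3, 77.8). All four match after rounding.

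**Assumptions not in the documents.** True subgroup PPRs are not given. I take a 20-point gap at 75/55, 85/65 and 90/70, with NSCLC (or the second ECOG group) lower. The upper end reflects the earlier SC preference rates of 85% and 91.5% cited in Protocol 2.2.1. The ECOG split is not given; I use 57/58 and 80/35 of 115.

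**Interval width.** The Clopper-Pearson limits are L = Beta(0.025; x, n − x + 1) and U = Beta(0.975; x + 1, n − x). Near an observed 70%, 29/41 gives 54.5 to 83.9% (29 points wide) and 22/32 gives 50.0 to 83.9% (34 points). Widths shrink to about 23-28 points near 85%.

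**Probability that two intervals overlap.** For independent binomials with probabilities b(·), sum b(i; n1, p1) × b(j; n2, p2) over all pairs (i, j) with U1(i) ≥ L2(j) and U2(j) ≥ L1(i).

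| Contrast (n1 v n2) | 75/55 | 85/65 | 90/70 |
|---|---|---|---|
| Melanoma v NSCLC (41 v 32) | 89% | 85% | 82% |
| Pooled adjuvant v NSCLC (83 v 32) | 81% | 74% | 66% |
| ECOG, even split (57 v 58) | 76% | 69% | 61% |
| ECOG, about 70/30 (80 v 35) | 80% | 73% | 65% |

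At 70/50 the ECOG 80/35 figure is 82%, the top of the ECOG range over these two splits. With no true gap, melanoma and NSCLC overlap more than 99% of the time.

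**Sensitivity to the unnamed interval method.** For melanoma v NSCLC at 70/50 and 85/65, Clopper-Pearson gives 89% and 85%, Wilson 86% and 80%, and Wald 82% and 75%.

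**What a difference would show.** The M&N 95% interval is the set of d with |p̂1 − p̂2 − d| / √{[p̃1(1 − p̃1)/n1 + p̃2(1 − p̃2)/n2] × N/(N − 1)} ≤ 1.96, where p̃1 and p̃2 are the maximum-likelihood rates constrained to differ by d, and N = n1 + n2.
- 29/41 v 22/32 (70.7% v 68.8%): −19 to +24 points.
- 58/83 v 22/32 (69.9% v 68.8%): −16 to +21 points.

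Near-identical observed rates would therefore still leave a gap of about 20 points open. The simple half-width 1.96 × √(p1q1/n1 + p2q2/n2), with q = 1 − p, gives a similar size for 41 v 32: 1.96 × √(0.21/41 + 0.25/32) = 22 points at 70/50, and 20 points at 85/65.

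**Would a test help?** A two-sided 5% score comparison of 41 v 32 has 43% power at 70/50 and 56% at 85/65 (exact enumeration). A test would not establish consistency either, so intervals are the right addition.

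**The case against.** The strongest reply is that this is a descriptive display in an estimation study. The intervals are labelled nominal, no listed objective concerns heterogeneity, and Protocol 4.2 speaks of evaluating preference in several tumor types, which per-type estimates do. The point estimates will be on the plot, so an observed 20-point gap would be visible whether or not the intervals overlap. Anyone with the counts can derive the differences. Their width comes from the sample size, not from the missing table.

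Much of this stands. It keeps the point minor and argues against adding tests. It does not remove the mismatch: a descriptive display should not be introduced as determining whether rates are consistent.

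Three stronger readings are tempting, and the documents do not support them:
- **That the sponsor will judge consistency by overlap.** Neither section states such a rule, or any other.
- **That the plot would almost always look consistent.** At 90/70 the overlap probabilities in the table are 61-82%, so the intervals separate in roughly a fifth to two-fifths of trials. With a 30-point gap (90/60), melanoma and NSCLC overlap only 49% of the time.
- **That 85-89% applies to every subgroup contrast.** It describes melanoma v NSCLC with Clopper-Pearson intervals at the first two rate pairs. Pooled adjuvant v NSCLC and both ECOG splits are lower.

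**Conclusion.** The point holds as a minor one. A comparative aim is stated and no comparative estimate is planned, so the planned output cannot support a statement that the PPR is consistent across ECOG or tumor type. This conclusion rests on the text alone. The overlap figures only show how weak an overlap reading would be, and they depend on assumed subgroup rates, an assumed ECOG split and Clopper-Pearson intervals. The subgroup sizes rest on the SAP's own dropout assumptions. On those sizes, a difference between an adjuvant tumor type and NSCLC would be known only to within about 20 points either way. A reader might infer that the primary result is compromised. It is not: the overall PPR and its interval do not depend on SAP 3.9.

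**What to change.** In SAP 3.9, and in Protocol 9.9 at the next amendment:

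1. Reword the aim as estimating how far the PPR differs by subgroup.
2. Add PPR differences with 95% M&N CIs for melanoma minus NSCLC, RCC minus NSCLC, and ECOG 0 minus ECOG 1. Pooled adjuvant minus metastatic NSCLC is optional, since that grouping is not among the listed subgroup variables. Label all of them descriptive. Apply the existing 10% rule, so that no ECOG difference is reported if one category is too small.
3. Name the method for the within-category intervals.
4. State that overlapping subgroup intervals are not evidence of consistency, and that differences up to the reported CI limits remain possible (about 20 points either way for an adjuvant tumor type v NSCLC).

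The cost is one table from data already collected, by a method the SAP already uses, plus a few words of text. The downside is that the table will show wide intervals, and the report could no longer rest a claim of consistency on the forest plot. The change belongs in a SAP amendment before final database lock; added later, the differences would be post hoc under SAP Section 3.
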